Academy of Neurology to be the first-line intervention for tics.⁶ Immediately prior to each CBIT session, participants will undergo TMS targeting the SMA. The specific type of TMS procedure will be randomly assigned between subjects and be either: 1 Hz repetitive TMS (rTMS), continuous theta burst stimulation (cTBS), or sham stimulation.

4.2. Drug/Device Handling:

TMS device. Stimulation will be delivered using a Magstim Super Rapid2 stimulator (Magstim Company Ltd, UK). The device will be used to deliver electromagnetic stimulation through a small coil positioned over a targeted area on the scalp. The manufacturer's indication for use is to stimulate peripheral nerves and the human cortex for diagnostic and research purposes.

We will use a Magstim air-cooled 70mm figure-eight coil for motor threshold determination and active TMS conditions. Sham stimulation will use the Magstim sham air-cooled coil, which produces auditory signals identical to an active coil but contains a mu-metal shield that diverts the majority of the magnetic flux such that a minimal (<3%) magnetic field is delivered to the cortex.

The device is installed and set-up at the University of Minnesota Non-Invasive Neuromodulation Laboratory (NINL). The device will only be able to be administered by trained personnel. The device is located in a locked, access controlled room.

[figure not shown]
Operation of the TMS device (MAGSTIM Super Rapid 2) will follow the procedures outlined in the attached "Operating Manual."

- 4.3. Biosafety: N/A
- 4.4. Stem Cells: N/A
- 4.5. Fetal Tissue: N/A

5. Procedures Involved

5.1. **Study Design**: The study is a double-blinded randomized control trial that will examine whether combining Comprehensive Behavioral Intervention for Tics (CBIT) with inhibition of the

PROTOCOL TITLE: Transcranial Magnetic Stimulation to Augment Behavior Therapy for Tics VERSION DATE: 2/24/2022

supplementary motor area (SMA) using transcranial magnetic stimulation (TMS) normalizes activity in the SMA-connected circuits, improves tic suppression ability, and enhances CBIT outcomes in young people with tic disorder. We will compare two rTMS procedures, 1 Hz rTMS and continuous theta burst stimulation (cTBS), against sham stimulation. Youth with chronic tics (n = 60) will complete 10 daily sessions of CBIT plus randomly assigned TMS procedure, with fMRI, behavioral, and clinical assessments before and after treatment and at 1 and 3 month follow-ups (figure 1).

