- Tic Suppression Task (TST) procedures: The TST will be our primary measure of behavioral target engagement. In this paradigm, a participant is seated alone in a room in front of a computer capturing a video recording of tic occurrences for later coding by independent raters. TST will consist of two 3-min conditions: 1) free-to-tic (FT): youth is instructed to stay seated and tic freely, a measure of naturally occurring tic frequency (tics per minute) ; 2) suppression: youth is instructed to suppress tics. Videos will be coded to establish tic frequencies using a computerized behavioral coding program.
- Neuroimaging procedures. MRI and fMRI data acquisition: A Siemens Prisma 3T scanner located at the Center for Magnetic Resonance Research (CMRR) will be used for image acquisition. To minimize motion artifact, we will immobilize the participant's head with foam wedges that fit snugly between the head and 32channel receive only head coil. As needed, we will re-run scans or bring back participants for a repeat scan session. We will acquire the following data: 3D T1 ME-MPRAGE, 3D T2 SPACE, resting fMRI, spin Echo fMRI reverse phase encode scan pair, finger tapping task. The Finger Tapping Task will be used for functional localization of SMA. This task is used to isolate neural activity in

PROTOCOL TITLE: Transcranial Magnetic Stimulation to Augment Behavior Therapy for Tics VERSION DATE: 2/24/2022

motor planning and execution areas, including SMA, and is a highly reliable, well-established fMRI task used for motor mapping⁵³ and for TMS targeting of motor cortex and SMA by our group and others.³³ A whole-brain activation map showing the contrast of rest vs. active tapping will be created for each person to determine the precise placement of the TMS coil.

- **Randomization:** Randomization will occur after pre-treatment assessments. Randomization will be stratified on baseline TST performance (tic suppressibility below or above 50%) and medication status (on vs. off).
- Intervention Protocol: CBIT+TMS. TMS will be delivered immediately prior to the start of CBIT sessions (see figure 2).
- **CBIT Protocol** will follow the published CBIT manual⁵⁴ tested in the large trials that established CBIT efficacy in children and adults.^{8,9} Participants will receive 10 sessions of CBIT, 1 session per

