- **Premature Termination.** At any time, participants may deteriorate or develop clinical exigencies that lead study staff to recommend additional out-of-protocol treatments above and beyond that provided by ASAP guidelines (e.g., change in medications during the study). Such participants will be considered "premature terminators" (PMT) and classified as a protocol violation. In order to enhance the ITT analyses, "prematurely terminated" participants will continue to be treated within their assigned treatment arms insofar as possible, and assessments will continue according to protocol.
- Analysis population will be an intent-to-treat population including all enrolled participants who completed at least 1 CBIT session.
- Treatment of Missing Data: All participants will remain

PROTOCOL TITLE: Transcranial Magnetic Stimulation to Augment Behavior Therapy for Tics VERSION DATE: 2/24/2022

in the study unless consent is withdrawn or there are concerns about patient safety. While there is little that can be done to address missing data when participants drop out during the training process itself, we can compare baseline characteristics of those who drop out at this time versus those who do not and adjust models based on significant predictors of dropout. For those who drop out during the follow-up period or miss some assessments during followup, we will use multiple imputation by chained equations (MICE) to allow for missing data without loss of those cases from the model under the assumption of Missing at Random (MAR). Sensitivity Analysis: If dropout status appears to be Missing Not At Random (MNAR), i.e., dropout is associated with an unobserved outcome, we will run sensitivity analyses using MICE to compare imputed and non-imputed models results to assess robustness of statistical inference.

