the stimulation groups, and baseline x group interactions. Random effects will be used to model within-subject variation from the first-level analyses. Altogether, the LME will allow us to model how the within-subject change in activation from pre-treatment to post-treatment differs across active and sham conditions. *In addition*, we will also investigate the effects of each TMS regimen on the connectivity in the entire CSTC. To this end, we will extract the ROI-level time courses from each region in the CSTC, and we will use partial correlations to obtain an estimate of connectivity between each ROI pair within the CSTC while accounting for the data observed in the other ROIs. Given the collection of partial correlations for each study participant, we will use the SPU test, which uses the collection of partial correlations simultaneously, to assess for group differences across the sham and TMS regimens.⁷⁵

- Aim 2. Target engagement: Behavior. Hypothesis: Either or both active TMS groups will show within-subject improvement (small effect size of at least Cohen's d = 0.3) in tic suppression ability as measured by the Tic Suppression Task (TST). TST "tic suppression ability" scores will serve as the primary outcome in an ANOVA model. An ANOVA will be used to establish if there exist differences in how the 1Hz, cTBS, and sham conditions affect change in tic suppression ability from pre- to post-treatment. Group indicators for these conditions will be the primary predictors for the model.
- Aim 3. Assess dose-response relationship. Changes in brain (Aim 1) and behavior (Aim 2) targets will be compared between active TMS groups (1Hz rTMS vs. cTBS) using ANOVA. In the case that both active TMS regimens are found superior to sham, we will compare the regimens on safety and feasibility. We will use 2-sample t-tests to compare the two regimens using data from our safety and feasibility measures and prioritize the regimen with significantly better (p<.05) outcomes.
- 15.2. Power Analysis: In Aim 1, hypothesis 1 our proposed sample size after accounting for expected attrition will give us 80% power to detect an effect size of at least $\eta^2=0.18$ for differences in SMA activation between active TMS and sham. For Aim 2, our proposed sample size will give us 80% power to detect an effect size of at least d = 0.90 for a within-subject improvement in tic suppression ability. Our preliminary data showed effect sizes of this magnitude.

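### Missing post-treatment outcomes after treatment-phase dropout are not imputed; covariates are instead chosen by a low-powered test against dropout, which costs precision and pre-specification more than it risks bias.

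*Combined protocol and SAP*

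**What the plan says.** Section 15.1 (Treatment of Missing Data) separates two periods. For the treatment period it begins "While there is little that can be done to address missing data when participants drop out during the training process itself", then proposes comparing the baseline characteristics of those who drop out with those who do not, in order to "adjust models based on significant predictors of dropout". It gives no candidate list, no significance level, and no statement of which models are affected. For the follow-up period it specifies MICE under a missing-at-random assumption. A sensitivity analysis, run if dropout appears not to be at random, sets imputed against non-imputed results.

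The same section defines the analysis population as intent-to-treat, covering everyone with at least one CBIT session. The target-engagement outcomes (sections 3.1 and 15.1) are changes from pre- to post-treatment. Post-treatment is a separate visit from the 1- and 3-month follow-ups (section 5.2, Timing).

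The Aim 1 mixed model includes baseline activation and its interaction with group. The Aim 2 ANOVA of change in TST score names only group indicators. Yet section 5.2 says "Randomization will be stratified on baseline TST performance", dichotomised at 50% suppressibility, and on medication status.

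**The concern.** A participant who leaves after session 3, say, is in the analysis population but has no post-treatment value unless an exit assessment supplies one. The plan's only primary remedy is a covariate adjustment chosen by a significance test. That raises three problems.

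- The test compares a handful of dropouts with everyone else, so it will usually miss a real predictor of moderate size.
- It selects on association with dropout. A covariate reduces bias or variance in the treatment comparison only if it also relates to the outcome.
- The covariate set of the primary models is settled by the data. The plan leaves out of Aim 2 the two variables it already considers important enough to stratify on.

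At stake are the precision and pre-specification of the primary comparisons. Some bias is also possible if dropout depends on prognosis differently in the three arms. That is not far-fetched: session lengths differ (33 minutes or 40 seconds, section 5.2), and a significant adverse reaction to TMS is a ground for withdrawal (section 12.1).

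**Working it through.** **Inputs from the documents.** Sample size: "Youth with chronic tics (n = 60) will complete 10 daily sessions of CBIT plus randomly assigned TMS procedure". Three arms: "1 Hz repetitive TMS (rTMS), continuous theta burst stimulation (cTBS), or sham stimulation". Stated power for Aim 1: 80% at η² = 0.18; for Aim 2: 80% at d = 0.90 (section 15.2).

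**Assumptions.** Equal allocation (20 per arm); dropout 6 to 12 of 60; two-sided 0.05 for the screen (p<.05 appears only in Aim 3); 15 to 20 candidate variables. Table 1 lists roughly 12 to 16 pre-treatment measures, some of which could supply more than one variable.

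**1. The plan's own figure.** Section 15.2 says "our proposed sample size after accounting for expected attrition will give us 80% power" but gives no attrition rate. For a three-group ANOVA the noncentrality is N × 0.18/0.82. Power is 0.800 at N = 47, 0.809 at N = 48 and 0.896 at N = 60. Aim 1 therefore fits about 12 or 13 losses, near the upper end of the assumed range. Aim 2, read as a comparison of two arms at d = 0.90, gives 0.792 with 20 per arm and 0.693 with 16, so it fits almost no attrition. The two do not settle on one rate, which is why a range is used.

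**2. Power of the screen.** Two-sample t test, noncentrality d × √(n₁n₂/60), 58 df.

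| Dropouts vs rest | √(n₁n₂/60) | d = 0.3 | d = 0.5 | d = 0.8 | d for 80% power |
|---|---|---|---|---|---|
| 6 vs 54 | 2.32 | 11% | 21% | 45% | 1.23 |
| 12 vs 48 | 3.10 | 15% | 33% | 68% | 0.92 |

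**3. False selections.** With K independent null candidates, P(at least one) = 1 − 0.95^K: 54% for K = 15 and 64% for K = 20. The expected number is 0.05K, or 0.75 to 1.0. Many Table 1 scales overlap. With pairwise correlation 0.3 to 0.5 (assumed), simulation gives about 36 to 46% for K = 15 and 42 to 55% for K = 20.

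**4. Share of selected variables that are noise.** With T true predictors among K, the share is 0.05(K − T)/[0.05(K − T) + T × power]. For K = 15 and d = 0.5:

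- T = 1, 6 dropouts: 0.70/(0.70 + 0.208) = 77%.
- T = 5, 12 dropouts: 0.50/(0.50 + 5 × 0.332) = 23%.

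**5. Effect on the treatment estimate.** Simulation: 3 arms of 20, 12 candidates, no true effect, 10 to 20% dropout, with one predictor (correlation 0.5 with outcome) driving dropout in the active arms only.

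| Analysis | Bias (SD units) | SE |
|---|---|---|
| Complete cases, unadjusted | −0.035 to −0.090 | – |
| Plan's rule | −0.030 to −0.051 | 0.33–0.35 |
| Predictor fixed in advance | within 0.007 of zero | 0.29–0.32 |

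The rule selected nothing in 29 to 47% of trials and found the true predictor in 18 to 50%. Type I error stayed at 0.046 to 0.059 throughout. At correlation 0.7 the bias left by the rule reached about 0.08 SD. When dropout depended on the predictor equally in all arms, no method was biased. Hand check of the SEs: with 18 per arm, √(2/18) = 0.333, and × √(1 − 0.25) = 0.289; with 16 per arm, 0.354 and 0.306.

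**6. Precision of the Aim 2 model.** With equal variances before and after, and pre-post correlation ρ, the SE ratio of ANCOVA to an ANOVA of change is √((1 + ρ)/2): 0.866 at ρ = 0.5 and 0.922 at ρ = 0.7 (ρ assumed). That is an SE 8 to 13% smaller for one degree of freedom.

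**7. What imputation adds.** With only the outcome missing and the same baseline covariates in both models, simulation gave bias of about 0.01 for both complete-case ANCOVA and MICE, and SEs of 0.298 and 0.301. MICE earns its place only if it uses information collected after baseline.

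**The case against.** The strongest reply is that the practical harm is slight and the plan already has partial safeguards. Aim 1 conditions on baseline activation. People who leave are encouraged to attend a last assessment (section 12.2), and prematurely terminated participants continue to be assessed. Table 1 appears to mark the TST at the treatment visits too, since its row has four marks where the YGTSS has three. Section 17.1 also mentions video recording at CBIT+TMS visits for the TST. So some early leavers may have usable tic-suppression data. The sensitivity analysis is not expressly confined to follow-up. The wording is also loose enough that part of the problem is missing detail.

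Most of this stands, and it limits the point. It does not remove it: the exit assessment omits MRI, the plan does not say that on-treatment or exit TST values enter the primary analysis, and comparing imputed with non-imputed results under a missing-at-random method does not test a departure from that assumption.

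Two stronger readings are tempting. A reader might infer that the rule selects mostly noise. The documents do not support that: the noise share runs from 23 to 77% in step 4, and the documents fix neither the candidates, the dropout count nor the threshold. A reader might also infer that the primary outcomes are left wholly uncorrected or seriously biased. The safeguards above, the partial correction in step 5 and the unaffected Type I error argue against that.

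**Conclusion.** The point holds in a limited form. For dropout during treatment, the plan does not impute the missing post-treatment primary outcomes, and it corrects for them at best partly, through a screen with 21 to 33% power for a moderate predictor and up to a 54 to 64% chance of at least one false selection. The likely bias is about 0.03 to 0.08 SD, which is small against a design powered for d = 0.90, and it is nil unless dropout works differently by arm. The surer loss is precision (SE 0.33–0.35 against 0.29–0.32 when an outcome-related covariate is fixed in advance) and a primary model that cannot be written down before the data are seen. These sizes rest on assumed dropout, allocation, threshold, candidate count and correlations, none of which the documents give. The structural findings rest on the text alone: selection by dropout, MICE specified only for follow-up, and no stratification factors named in the Aim 2 model.

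**What to change.** Replace the screening rule in section 15.1 with covariates fixed in advance.

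- **Aim 2:** ANCOVA of post-treatment TST score on group, baseline TST and medication status.
- **Aim 1:** keep baseline activation and add the two stratification factors (TST suppressibility stratum and medication status).
- **Imputation:** extend the planned MICE to the post-treatment visit, with arm, these covariates, baseline YGTSS, and any on-treatment or exit TST values as auxiliaries. Confirm at which treatment visits the TST is recorded. Without post-baseline auxiliaries, MICE adds little to complete-case ANCOVA, and the SAP should say so.
- **Dropout comparison:** report it by arm, descriptively, without letting it change the primary models.

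The cost is SAP wording and a few fixed degrees of freedom. The baseline variables are already collected and MICE is already planned. None of this addresses dropout that is not at random, which would need a separate sensitivity analysis.

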Stimulation context tracking form	TMS operator completed form to track behavior and participant self-reported emotional state during rTMS stimulation		x			2
Blinding form (parent, staff, and child)	Assess belief about whether participant got active or placebo TMS			x	x	2
Concurrent Treatment Tracking Form	Record of all medications and dosages, psychotherapy	х	x	x	x	5
Client Satisfaction Quesitonnaire ⁵²	Assess patient satisfaction with the intervention			x		2
MRI	T1 and T2 structural, rs-fMRI, finger tapping task for TMS coil placement	х		x		60

• MINI 7: The Mini International Neuropsychiatric Interview (MINI) is a short, structured diagnostic interview, and is the most widely used neuropsychiatric diagnostic assessment tool in the world. The MINI is a tool used to conduct neuropsychiatric screening, diagnostic interviews, and outcome tracking for the most common adult and childhood DSM-5 and ICD-10 psychiatric

PROTOCOL TITLE: Transcranial Magnetic Stimulation to Augment Behavior Therapy for Tics VERSION DATE: 2/24/2022

[figure not shown]
disorders. The MINI has been validated against the longer Structured Clinical Interview for DSM diagnoses (SCID-P) and against the longer Composite International Diagnostic Interview for ICD-10 (CIDI), and has been used in clinical care and research for more than 25 years. A digital version of the MINI 7 by Nview is available to researchers in the Department of Psychiatry & Behavioral Sciences and will be used. This program allows access to the MINI via web browser and stores data in HIPPA-safe Nview servers. Participant IDs will be indicated on MINI digital forms.

[figure not shown]
- IQ assessment: If subjects have not completed an IQ test within the previous 24 months from Step 2, they will complete a brief IQ test to determine eligibility for the study using either the Wechsler Abbreviated Scale of Intelligence, version 2 (WASI-2) or the Stanford-Binet Intelligence Scales, Fifth Edition (SB-5) (15 min).
- **Pregnancy testing:** Females who could potentially be pregnant will be tested for pregnancy and, if positive, will not be allowed to participate. If testing is refused, participation will not be allowed.

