- Motor threshold (MT) determination. Resting MT will be defined as the minimum magnetic flux needed to elicit a threshold EMG response (≥50 mV in peak-to-peak amplitude) in a resting target muscle (abductor pollicis brevis) in 5/10 trials using single-pulse TMS administered to the contralateral hand area of primary motor cortex. The MT procedure will occur during the first CBIT+TMS visit and this MT will be used to calculate stimulation intensity for all TMS sessions. Stimulation intensity may be adjusted to improve tolerability; all such adjustments will be reviewed by a study physician and documented.
- rTMS coil positioning: Individualized using fMRI and electric field modeling. TMS effects strongly depend on the spatial distribution of the induced electric field in the brain.⁶⁴ TMS targeting will be based on individual-level identification of the optimized coil location and orientation that induces the strongest electric field within SMA that show the highest parametric fMRI activation during the bilateral finger tapping task. This approach accounts for individual differences in physiology, which are prominent in developmental samples. We will create individual finite element method (FEM) models for each participant using the computer program SimNIBS (Danish Research Center for Magnetic Resonance, Copenhagen, Denmark and the Technical University of Denmark (Kgs Lyngby, Denmark) and participant anatomical MRIs, following procedures established by Co-I [name].65-67 Coil placement. The coil placement and orientation will be based on the individual models and continually monitored using a stereotaxic neuronavigation system (BrainSight 2.3.5, Rogue Research, Montreal, Quebec, Canada) running on an Intel-based Macintosh computer (Apple, Inc, Cupertino, CA). This

PROTOCOL TITLE: Transcranial Magnetic Stimulation to Augment Behavior Therapy for Tics VERSION DATE: 2/24/2022

system permits targeting of individual cortical locations using individual structural and functional MRI.

- TMS administration. TMS parameters are as follows:
 - Pulse frequency: 1 Hz, cTBS, or sham (randomized between subjects)
 - Pulse sequence:
 - 1 Hz: single train of 2000 pulses at 110% resting motor threshold (33 min duration)
 - cTBS: bursts of 3 pulses at 30 Hz repeated every 200ms (5 Hz burst frequency), single uninterrupted 40 sec train, 600 total pulses at 90% resting motor threshold (40 sec duration)

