• Aim 1. Target engagement: Brain. 1) Primary measure of neural target engagement will be decreased activation in SMA. Hypothesis 1: Either or both active TMS groups will demonstrate within-subject decrease (effect size $\eta 2=0.18$ in an ANOVA) in SMA activation post-treatment, as measured with an fMRI finger tapping task. While this is a large effect size in practice, we point out that Wu et al (2014) observed a much larger effect size of η 2=0.41 in the decrease in SMA activity comparing active vs sham cTBS. 2) Secondary measure of neural target engagement will be change in fMRI resting state functional connectivity of at least one SMA-mediated circuit (SMA-DLS, SMA-M1). Hypothesis 2: Either or both active TMS groups will demonstrate within-subject change (effect size $\eta 2=0.18$ in an ANOVA) in resting state fMRI connectivity (RSFC) of at least one SMA-mediated circuit (SMA-DLS, SMA-M1) post-treatment. A region of interest (ROI) analysis will be performed to determine the time*treatment group differences in SMA activation elicited by an fMRI motor task (finger tapping). The SMA ROI will be identified by placing a seed (sphere with 5mm radius) that matches the coordinate used for individual TMS coil placement. Activation parameters in the SMA will be identified in a first-level analysis, using a general linear model (GLM) to model each subject's SMA time course during the motor task. These activation parameters will be used in a subsequent linear mixed effects (LME) model. The predictors of the LME will include the baseline activation, group indicators for

PROTOCOL TITLE: Transcranial Magnetic Stimulation to Augment Behavior Therapy for Tics VERSION DATE: 2/24/2022

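### Aim 1 measures SMA activation at a site chosen for high baseline activation, so a within-arm fall is expected without any treatment effect; the active-versus-sham contrast is not biased, but Hypothesis 1 is worded within-subject

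*Combined protocol and SAP*

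**What the plan says.** - **Target.** Under Neuroimaging procedures (section 5.2), a rest-versus-tapping activation map "will be created for each person to determine the precise placement of the TMS coil". Under rTMS coil positioning (section 5.2), the coil location and orientation are those "that induces the strongest electric field within SMA that show the highest parametric fMRI activation during the bilateral finger tapping task", found with an individual electric-field model.
- **ROI.** Section 15.1, Aim 1: "The SMA ROI will be identified by placing a seed (sphere with 5mm radius) that matches the coordinate used for individual TMS coil placement".
- **Measure and hypothesis.** Section 15.1, Aim 1: "Primary measure of neural target engagement will be decreased activation in SMA". Hypothesis 1 continues: "Either or both active TMS groups will demonstrate within-subject decrease", assessed after treatment with the finger-tapping task.
- **Scans.** The MRI row of Table 1, marked before and after treatment, lists "T1 and T2 structural, rs-fMRI, finger tapping task for TMS coil placement". No second localiser run, no split of the tapping data and no anatomical ROI is described.
- **Model and power.** The Aim 1 mixed model uses baseline activation, group and their interaction, and its stated purpose is to compare pre-to-post change between active and sham. Section 15.2 powers Aim 1 for an active-versus-sham difference of η² = 0.18.

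**The concern.** The place where the outcome is read is chosen because tapping activation looked high there at baseline, and the baseline value appears to come from that same acquisition. Part of any observed peak is scan noise that happened to be positive. That noise enters the baseline value but not the post-treatment value, so activation should drop on the second scan even if nothing was done.

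This bias points the same way as Hypothesis 1. A drop within an active arm could be reported as neural target engagement when selection alone explains it. A drop in the sham arm could likewise be read as behaviour therapy normalising SMA, since every arm receives that therapy and section 1.1 asks about normalisation of SMA-connected circuits.

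**Working it through.** **1. The plan's own figure.** Inputs: η² = 0.18 and 80% power (section 15.2); 60 participants (sections 5.1 and 10.1). Attrition, allocation ratio and the Aim 1 alpha are not stated. I assume equal allocation and alpha 0.05, the only level given (Aim 3). For a three-group F test, f² = 0.18/(1 − 0.18) = 0.2195 and λ = f² × N.

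| N | λ | Power |
|---|---|---|
| 60 | 13.17 | 0.896 |
| 54 | 11.85 | 0.858 |
| 48 | 10.54 | 0.809 |
| 40 | 8.78 | 0.723 |

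The smallest N giving 80% is 48. The stated power therefore fits 20% attrition (60 × 0.8 = 48, or 16 per arm), but cannot be strictly reproduced without the missing inputs. It is consistent with a between-group test. The point below does not depend on it.

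**2. Direction of the bias.** Let T(s) be stable activation at location s, and e1(s), e2(s) independent zero-mean scan noise before and after treatment. The location s* is chosen where T + e1 is high. With no treatment effect, the expected change at s* is E[e2(s*)] − E[e1(s*)] = 0 − E[e1(s*)]. This is negative, because choosing a high value favours locations where e1 is positive. Nothing in it depends on arm. If s* is located on data independent of the baseline measurement, E[e1(s*)] = 0 and the bias vanishes. Moving the coordinate off the peak, as the electric-field step may do, weakens the effect.

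**3. Illustrative size with no treatment effect.** Assumptions, none from the documents: SMA search box 24 × 32 × 24 mm; 2 mm voxels; stable map smoothed at 10 mm and noise at 6 mm FWHM; voxel reliability 0.4, 0.6 or 0.8; a 5 mm sphere centred 0, 4 or 8 mm from the baseline peak, the offset standing in for the electric-field step; 1,200 simulated participants per scenario. Here dz is mean change divided by the SD of change. P is the chance that a two-sided 5% paired test in one arm shows a significant decrease (0.025 nominal in that direction).

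| Reliability | Offset (mm) | Change | dz | P, n = 16 | P, n = 20 | dz, independent localiser |
|---|---|---|---|---|---|---|
| 0.8 | 0 | −0.35 | −0.86 | 0.90 | 0.96 | −0.03 |
| 0.6 | 0 | −0.65 | −1.16 | 0.99 | 1.00 | −0.02 |
| 0.4 | 0 | −0.93 | −1.44 | 1.00 | 1.00 | 0.05 |
| 0.8 | 4 | −0.25 | −0.60 | 0.61 | 0.72 | 0.00 |
| 0.6 | 4 | −0.48 | −0.80 | 0.84 | 0.92 | −0.01 |
| 0.4 | 4 | −0.66 | −0.97 | 0.95 | 0.98 | −0.01 |
| 0.8 | 8 | −0.10 | −0.23 | 0.14 | 0.17 | 0.01 |
| 0.6 | 8 | −0.18 | −0.28 | 0.18 | 0.22 | −0.05 |
| 0.4 | 8 | −0.27 | −0.36 | 0.27 | 0.33 | 0.03 |

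Example: at reliability 0.8 and 4 mm, the non-centrality is −0.60 × √16 = −2.40, and P is the probability that this non-central t on 15 df falls below its lower 2.5% critical value, 0.61. On the peak, the proportional drops (0.35/1.76 = 20%, 0.65/1.67 = 39%, 0.93/1.63 = 57%) lie close to 1 − reliability, as regression to the mean predicts.

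**4. The between-arm contrast.** In 4,000 resampled null trials per reliability level (N = 48, ROI on the peak), type I error was 0.049 to 0.054 for a change-score ANOVA and 0.050 to 0.054 for an ANCOVA on baseline. The ANCOVA omitted the baseline-by-group terms of the planned model. The reason is general: randomisation follows the pre-treatment assessments, and selection works identically in all arms.

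**The case against.** The strongest reply is that the plan never tests a within-arm fall. Its ROI analysis is a time-by-treatment comparison, the mixed model contrasts active with sham, the power statement does the same, and the earlier result cited beside Hypothesis 1 is itself active versus sham cTBS. Aim 2 also speaks of within-subject improvement and then tests it across the three conditions, so the phrase may simply name the change score. All of this stands, and it means much of the remedy is already in the model.

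It does not settle the matter. Nothing in the plan says that the between-arm contrast alone decides Hypothesis 1, whose wording would be met by a fall in one active arm. Section 3.1 also words target engagement as within-subject change.

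Three stronger readings are tempting and unsupported:
- **That the active-versus-sham comparison is invalid.** It is not; the selection effect is common to all arms.
- **That the probabilities above are the trial's false-positive rate.** They belong to a paired test that the plan does not specify, on reliability and offset values that the documents do not give.
- **That the trial intends to credit a sham-arm fall to behaviour therapy.** No sham-only analysis is planned; this is only a risk of interpretation.

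Two limits remain. The documents do not expressly say that the localising run and the baseline outcome run are the same; that is inferred from the single task listed. Section 3.1 names resting-state connectivity as the primary neural endpoint, whereas section 15.1 ranks tapping activation first. That is a separate inconsistency; this point concerns tapping activation only.

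**Conclusion.** The concern holds for within-subject change and for the wording of Hypothesis 1, and no further. If one pre-treatment tapping acquisition both sets the coordinate and supplies baseline, a pre-to-post fall is expected in every arm with no treatment effect, in the direction of the hypothesis. All nine simulated scenarios showed a fall, and an independent localiser brought dz to between −0.05 and 0.05. The size could be modest or large: it depends on scan reliability and on how far electric-field modelling moves the coordinate from the activation peak. The planned between-arm inference survives, so this should be corrected but does not undermine the main analysis.

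**What to change.** 1. Reword Hypothesis 1 so that it is judged only on the baseline-adjusted active-versus-sham difference in SMA activation, in line with the mixed model and the power statement.
2. Wherever pre-to-post change is estimated or reported, locate the ROI on one half of the baseline tapping blocks and measure baseline on the other half, or use an anatomical SMA ROI. A sphere at the electric-field peak is not a substitute, because the field is steered by the same baseline map.
3. If a separate localiser run exists, say so, and say which run supplies baseline.

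Coil targeting stays as written. The cost is some rewording, a small change to first-level processing, and either a somewhat noisier baseline (split-half) or a less individual ROI (anatomical). No extra scanning is needed.
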